8.3.7. Recording and Follow-up of an AE and/or SAE

The investigator is responsible for ensuring that all AEs and SAEs are recorded in the eCRF and reported to the Sponsor.

Solicited ARs will be collected from Day 1 through 7 days after each dose (Part A). Other (unsolicited) AEs will be collected from Day 1 through 28 days after each dose in Part A (all participants) and Part C (only those who receive the BD).

Both MAAEs and SAEs will be collected from Day 1 throughout the entire study duration (Day 759 for all participants), as specified in the SoEs ([Table 16](#), [Table 17](#), [Table 18](#), [Table 19](#), [Table 21](#), [Table 22](#), and [Table 23](#)). Any AEs occurring before receipt of IP will be analyzed separately from TEAEs.

At every study site visit or telephone contact, participants will be asked a standard question to elicit any medically related changes, including surveillance for COVID-19 symptoms, in their well-being according to the scripts provided. Participants will also be asked if they have been hospitalized, had any accidents, used any new medications, changed concomitant medication regimens (both prescription and over-the-counter medications), or had any non-study vaccinations.

In addition to participant observations, physical examination findings or other documents relevant to participant safety classified as an AE will be documented on the AE page of the eCRF.

After the initial AE/SAE report, the investigator is required to proactively follow each participant at subsequent visits/contacts. All AEs and SAEs will be treated as medically appropriate and followed until resolution, stabilization, the event is otherwise explained, or the participant is LTFU (as defined in [Section 7.4](#)).

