9.5.2.1. Adverse Events

Safety and reactogenicity will be assessed by clinical review of all relevant parameters. Safety analyses will be provided for Parts A, B, and C separately unless specified otherwise.

The number and percentage of participants with any solicited local AR, with any solicited systemic AR, and with any solicited AR during the 7-day follow-up period after each dose will be provided only for Part A. A 2-sided 95% exact CI using the Clopper-Pearson method will be also provided for the percentage of participants with any solicited AR for each treatment group. Analysis of solicited AR will be provided using the Solicited Safety Set for Part A.

The number and percentage of participants with unsolicited AEs (Part A [all participants] and Part C [only those who receive the BD]), SAEs, MAAEs, AESIs (Part C [only those who receive the BD]), and AEs leading to discontinuation from IP or withdrawal from the study will be summarized. Unsolicited AEs will be presented by MedDRA preferred term and system organ class. Analyses of AEs will be provided for Part A and Part B using the Safety Set. For Part C, analysis of AEs will be provided in the Part C Safety Set (ie, participants who received booster in Part C).

For all other safety parameters, descriptive summary statistics will be provided, and [Table 12](#) summarizes the analysis strategy for safety parameters. Further details will be described in the SAP.

Table 12: Analysis Strategy for Safety Parameters in Part A

Safety Endpoint	Number and Percentage of Participants, Number of Events	95% CI
Any Solicited AR (Part A; overall and by local, systemic)	X	X
Any Unsolicited AE	X	
Any SAE	X	
Any Unsolicited MAAE	X	
Any Unsolicited Treatment-Related AE	X	
Any Treatment-Related SAE	X	
Discontinuation due to AE	X	
Any Grade 3 and above AE	X	
Any Treatment-Related Grade 3 and above AE	X	

Abbreviations: AE = adverse event; AR = adverse reaction; CI = confidence interval; MAAE = medically attended adverse event; MedDRA = Medical Dictionary for Regulatory Activities; SAE = serious adverse event.

Notes: 95% CI using the Clopper-Pearson method, X = results will be provided. Unsolicited AEs will be summarized by System Organ Class and Preferred Term coded by MedDRA. Safety parameters will be analyzed in applicable study parts and participants as further specified in the statistical analysis plan.

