Window Allowance (Days)	-28		+3	+3	+3	-3/+7	+3	+3	+3	-3/+7
Days Since Most Recent Vaccination	-	0	7	14	21	28/0	7	14	21	28
Safety Assessments										
eDiary activation for recording solicited adverse reactions (7 days) ⁶		X				X				
Review of eDiary			X				X			
Follow-up safety ⁷			X	X	X		X	X	X	
Recording of unsolicited AEs		X	X	X	X	X	X	X	X	X
Recording of MAAEs, AE leading to withdrawal, and concomitant medications relevant to or for the treatment of the MAAE ⁸		X	X	X	X	X	X	X	X	X
Recording of SAEs and concomitant medications relevant to or for the treatment of the SAE ⁸	X	X	X	X	X	X	X	X	X	X
Recording of concomitant medications and non-study vaccinations ⁸		X	X	X	X	X	X	X	X	X

Abbreviations: AE = adverse event; AR = adverse reaction; C = clinic visit; COVID-19 = coronavirus disease 2019; D = day; eDiary = electronic diary; FDA = Food and Drug Administration; ICF = informed consent form; M = month; MAAE = medically attended AE; NP = nasopharyngeal; RT-PCR = reverse transcriptase polymerase chain reaction; SAE = serious adverse event; SARS-CoV-2 = severe acute respiratory syndrome coronavirus 2; SC = safety (phone) call.

Note: In accordance with FDA Guidance on Conduct of Clinical Trials of Medical Products during the COVID-19 Pandemic (DHHS 2020a), investigators may convert study site visits to telemedicine visits with the approval of the Sponsor. All scheduled study visits should be completed within the respective visit windows. If the participant is not able to come on-site for a study site visit as a result of the COVID-19 pandemic (self-quarantine or disruption of study site activities following business continuity plans and/or local government mandates for “stay at home” or “shelter in place”), a safety call to the participant should be made in place of the study site visit. The safety call should encompass all scheduled visit assessments that can be completed remotely, such as assessment for AEs and concomitant medications (eg, as defined in scheduled biweekly safety phone calls). Home visits will be permitted for all non-dosing visits except for Screening if a participant cannot come to the study site as a result of the COVID-19 pandemic.

1. Day 0 and Day 1 may be combined the same day. Additionally, the Day 0 visit may be performed over multiple visits if within the 28-day screening window.

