6.6.1.5. Subgroup Analysis of TEAEs

An overview of TEAE, TEAE summaries presented by SOC and PT will be provided for the following subgroups:

- Age group (<65, and ≥ 65 years)
- Sex (male, female)
- Baseline SARS-CoV-2 status

These summaries may be provided for subgroups of select baseline characteristics.

6.6.1.6. Summary of AEs in Part B at the Final Analysis of Blinded Data

In Part B, for participants who were randomized to Placebo and requested mRNA-1273, SAE, MAAEs, and AE leading to withdrawal are collected throughout Part B.

At the time of the final analysis of blinded data (from the blinded phase of the study) (Section 6.4.3), in addition to the planned analysis of safety for the blinded phase (Part A), summary of SAE, MAAEs, and AE leading to withdrawal in Part B may be provided. The summary will be provided using the Part B groups during the Part B analysis period for safety as described in the table below.

Table 5: Part B groups and analysis period for safety

Part B Cohort	Description	Part B Analysis Period for Safety
mRNA-1273	Participants received at least one dose of mRNA-1273 in the Blinded Phase	From PDV/unblinding to earlier (data cutoff date for safety, last observed in Study). If a participant received mRNA-1273 in Part B, from 1 st date of study IP in Part B to earlier date of (data cutoff date for safety, last observed in Study).
Placebo	Participants only received Placebo in the Blinded Phase and did not receive mRNA-1273 in Part B	From PDV/unblinding to earlier date of (data cutoff date for safety, last observed in Study)

Placebo-mRNA-1273	Participants only received Placebo in the Blinded phase and received mRNA-1273 in Part B	From first dose of mRNA-1273 in Part B to earlier date of (data cutoff date for safety, last observed in Study)
-------------------	--	---

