3.1.2. Safety Endpoints for Primary Safety Objective

The primary safety objective will be evaluated by the following safety endpoints:

- Solicited local and systemic adverse reactions (ARs) through 7 days after each dose of IP (Part A: Blinded Phase only).
- Unsolicited adverse events (AEs) through 28 days after each dose of IP (Part A: Blinded Phase only).
- Medically-attended AEs (MAAEs) or AEs leading to withdrawal through the entire study period.
- Serious AEs (SAEs) throughout the entire study period.

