Booster 50 µg	Participants randomized in the blinded phase and received booster 50 µg in Part C Date of reference: date of booster	From dose date in Part C to earlier date of (DBL or data cutoff date for safety, last observed in study ^a).
Not received booster	Participants randomized to/received mRNA-1273 in Part A or B and did not receive booster in Part C Date of reference: date of BD-visit 1	Up to earlier date of (DBL or data cutoff date for safety, last observed in study ^a).
Placebo	Participants randomized to/only received Placebo in Part A or B and did not receive booster in Part C Date of reference: date of BD-visit 1	From BD-visit 1 in Part C to earlier date of (DBL or data cutoff date for safety, last observed in study ^a).
Effectiveness, Immunogenicity of mRNA-1273 primary Series		
mRNA-1273	Participants randomized to mRNA-1273 in the Blinded Phase	From Dose 1 of mRNA-1273 to earlier date of (booster date, DBL or data cutoff date, last observed in study ^a).
Placebo-mRNA-1273	Participants randomized to Placebo and received mRNA-1273 in Part B	
Safety of mRNA-1273 primary Series		
mRNA-1273	Participants received mRNA-1273 in the Blinded Phase	From Dose 1 of mRNA-1273 to earlier date of (booster date, DBL or data cutoff date, last observed in study ^a).
Placebo-mRNA-1273	Participants received Placebo in the Blinded phase and received mRNA-1273 in Part B	

^a last observed in study is the earliest date of study discontinuation, study completion, or death.

All analyses will be conducted using SAS Version 9.4 or higher unless otherwise specified.

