5.4.1. Unsolicited Treatment-emergent Adverse Events

A treatment-emergent AE (TEAE) is defined as any event occurring during the study not present before exposure to the IP or any event already present that worsens after exposure

to study vaccine. Worsening of a pre-existing condition after vaccination will be reported as a new AE.

Adverse events will also be evaluated by the investigator for the coexistence of MAAE which is defined as an AE that leads to an unscheduled visit to a healthcare practitioner.

Unsolicited AEs will be coded by PT and SOC using MedDRA and summarized by vaccination group.

All summary tables (except for the overall summary of AEs) for unsolicited AEs will be presented by SOC and PT or by PT only for TEAEs with counts of subjects included. SOC will be displayed in internationally agreed order.

When summarizing the number and percentage of subjects with an event, subjects with multiple occurrences of the same AE or a continuing AE will be counted once. Only the maximum severity level will be presented in the severity summaries, and the strongest relationship level will be presented in the relationship summaries. Percentages will be based upon the number of subjects in the Safety Set within each treatment cohort.

Unsolicited TEAEs will be summarized for Part B, Part C, and Primary Series using analysis periods as defined in Section 5.1.

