5.4.1.1. Overview of Unsolicited TEAEs

An overall summary of unsolicited TEAEs including the number and percentage of subjects by treatment cohort who experience the following will be presented:

- Any unsolicited TEAEs
- Any serious AEs
- Any unsolicited AEs that are medically-attended
- Any unsolicited TEAEs leading to discontinuation from participation in the study
- Any unsolicited TEAEs that are fatal
- Any unsolicited AEs that are Grade 3 or higher

- Any non-serious TEAE
- Any non-serious TEAEs that are Grade 3 or higher

The table will also include number and percentage of subjects with unsolicited TEAEs that are treatment-related in each of the above categories.

In addition, separate listings containing individual subject adverse event data may be provided.

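### The Part B/C SAP plans all-unsolicited TEAE tables for Part B and the primary series, but after open-label doses only SAEs, MAAEs and AEs leading to withdrawal are systematically collected

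*SAP*

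**What the plan says.** **Analysis.** Section 5.4.1 of the Part B/C SAP states: "Unsolicited TEAEs will be summarized for Part B, Part C, and Primary Series using analysis periods as defined in Section 5.1". Section 5.4.1.1 adds overview rows that include Grade 3+ events and "Any non-serious TEAE", each also shown for treatment-related events. Section 5.4.1.2 repeats the all-unsolicited, related and severe categories by system organ class and preferred term. For the primary series, Section 5.1.4 names two groups, mRNA-1273 and Placebo-mRNA-1273. Table 1 in Section 5.1.5 describes the second group for safety as "Participants received Placebo in the Blinded phase and received mRNA-1273 in Part B" and starts its period at the first dose of mRNA-1273.

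**Collection.** Protocol Section 8.3.7 says "Other (unsolicited) AEs will be collected from Day 1 through 28 days after each dose in Part A (all participants) and Part C", with Part C limited to booster recipients. Protocol Section 9.5.2.1 plans to summarise "The number and percentage of participants with unsolicited AEs (Part A [all participants] and Part C [only those who receive the BD"], again without Part B. For placebo participants who asked for vaccine, the Part A SAP (Section 6.6.1.6) says "SAE, MAAEs, and AE leading to withdrawal are collected throughout Part B". The Part B/C SAP's own endpoint list, Section 3.1.2, has "Unsolicited adverse events (AEs) through 28 days after each dose of IP (Part A: Blinded Phase only").

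**The concern.** The SAP asks for tables of a category of event that the study did not set out to collect in one of the two cohorts shown. A participant with an ordinary, non-serious event after an open-label dose, and no healthcare contact, has no scheduled route into the database. The same event after a Part A dose does. The table would present the two percentages side by side under one row label, so a lower crossover percentage could be taken as better tolerability when it reflects less collection.

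The Part B/C SAP warns in Section 3.5.1 that solicited reactions are not collected in the open-label phase, but gives no such warning for unsolicited events. Section 1 says the SAP prevails where it differs from the protocol, and Section 6, on changes from the protocol's analyses, reads as not applicable. The mismatch therefore governs the output and is not declared.

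**Working it through.** No sample size, power or event figure is at issue, so there is no stated number to reproduce. The check sets the collection rules beside the analysis rules.

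| Protocol schedule | Doses covered | Row "Recording of unsolicited AEs" | Safety call asks for unsolicited AEs |
|---|---|---|---|
| Table 16 | Part A, both doses | Present | Yes |
| Table 21 | Open-label doses, placebo crossovers | Absent | No |
| Table 22 | Open-label dose, one-dose mRNA-1273 participants | Absent | No |
| Table 23 | Part C booster | Present (booster recipients) | Yes |

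1. *Which doses feed the Placebo-mRNA-1273 column?* Its period starts at the first mRNA-1273 dose, which is given in Part B. All its vaccine exposure before the booster therefore falls under Table 21, where only MAAEs, SAEs and AEs leading to withdrawal have rows.
2. *Which doses feed the mRNA-1273 column?* Mainly Part A doses under Table 16, with scheduled 28-day collection of all unsolicited AEs.
3. *Which rows are affected?* Those that go beyond the three collected categories: any unsolicited, non-serious, severe or Grade 3+, and treatment-related TEAEs. The SAE, MAAE and withdrawal rows rest on the same collection in both cohorts.
4. *Does the analysis window help?* No. The Part A SAP (Section 6.1) uses 28 days after any vaccination as its primary safety period. Table 1 of the Part B/C SAP runs the primary-series period to booster, cutoff or last observation, with no 28-day limit. Even the mRNA-1273 column therefore mixes a period of full collection with a longer one of partial collection.
5. *Part B tables.* Under the schedules, all three Part B cohorts have only the three collected categories. The comparison between them is not biased by study part, but a row labelled any unsolicited TEAE would mostly restate those three categories under a broader name.

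**Illustration of size.** Let r be the true proportion with any unsolicited TEAE, and c the share of those participants who also have an SAE, MAAE or AE leading to withdrawal. The documents give neither, so both are assumptions.

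Proportion shown for the crossover cohort = c × r.

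With r = 20%:
- c = 0.25: 0.25 × 20% = 5%
- c = 0.50: 0.50 × 20% = 10%
- c = 0.75: 0.75 × 20% = 15%

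For any r, the cohort shows 25% to 75% of its true proportion over this range of c. With the same true r and complete 28-day capture, the mRNA-1273 cohort would show 20%.

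**The case against.** Several protocol passages point the other way. Section 8.2.1 cites Table 21 among the schedules under which AEs are collected by safety call. Section 8.3.11 has every unsolicited AE that is reported or observed in the study recorded, without limit by part. Section 8.3.7 has a standard question about medical changes asked at every contact, and Section 9.5.2.1 provides AE analyses for Part B as well as Part A. Some ordinary unsolicited AEs may therefore be in the Part B data, and deleting tables outright could hide them. This stands as a reason to reconcile the passages and keep recorded events visible. It does not show systematic collection: Table 21's own call content omits unsolicited AEs, and uneven passive capture cannot be read as a rate.

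Three stronger readings are tempting, and the documents do not support them.

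- *That a pooled primary-series rate will be diluted.* No such column is specified. Safety tables are by cohort, Section 5.4.1 takes percentages within cohort, and Section 5.1.4 names an overall group only for Part C.
- *That crossover rates will be close to zero.* MAAEs include any unscheduled healthcare visit, telemedicine included (protocol Section 8.3.2), and can be non-serious. Clinically significant findings at open-label visits are also reported as MAAEs. The disputed rows will hold these events.
- *That the primary safety objective is distorted.* Part A safety has been analysed and reported (Part B/C SAP Section 1). The primary safety endpoints that run through Part B are the ones Part B collects.

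The primary-series safety tables are also descriptive. Section 5.4 of the Part B/C SAP plans no between-cohort test or ratio, whereas the Part A SAP planned rate ratios. This limits the harm but leaves the misleading side-by-side display.

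**Conclusion.** Wrong as written. The any-unsolicited, non-serious, severe or Grade 3+ and treatment-related TEAE rows for Placebo-mRNA-1273 in the primary-series tables will be under-ascertained and cannot be compared with the mRNA-1273 cohort. The same rows in the Part B tables carry a label broader than their content. The direction follows from the collection rules. The size cannot be derived from the documents, and the 5% to 15% against a true 20% rests wholly on the assumed c and r. The conclusion also assumes that sites followed Tables 21 and 22; if some followed the broader recording text, capture would be higher but uneven, and the rates still not comparable. The problem is confined to Part B and primary-series safety reporting and leaves the reported Part A safety results untouched.

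**What to change.** In the Part B/C SAP:

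- Restrict the any-unsolicited, non-serious, severe or Grade 3+ and treatment-related TEAE tables to the 28-day windows for mRNA-1273 in Part A and the booster in Part C.
- For Part B and Placebo-mRNA-1273, present SAEs, MAAEs and AEs leading to withdrawal as the rows that rest on like collection.
- Show any other recorded AEs after open-label doses only in a listing, or in a row footnoted as not systematically collected.
- State that no total column across the two primary-series cohorts will be produced for the affected categories.
- Correct Section 3.1.2 to include Part C booster recipients, as protocol Table 1 does.
- Record the departure from protocol Section 9.5.2.1 in Section 6.

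In the protocol, or in a note to the SAP, reconcile Sections 8.2.1 and 8.3.11 with Section 8.3.7 and Table 21.

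The cost is wording and fewer or relabelled table rows. No new data are needed, and listing what was recorded means no safety information is lost.

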5.4.1.1. Overview of Unsolicited TEAEs

An overall summary of unsolicited TEAEs including the number and percentage of subjects by treatment cohort who experience the following will be presented:

- Any unsolicited TEAEs
- Any serious AEs
- Any unsolicited AEs that are medically-attended
- Any unsolicited TEAEs leading to discontinuation from participation in the study
- Any unsolicited TEAEs that are fatal
- Any unsolicited AEs that are Grade 3 or higher

- Any non-serious TEAE
- Any non-serious TEAEs that are Grade 3 or higher

The table will also include number and percentage of subjects with unsolicited TEAEs that are treatment-related in each of the above categories.

In addition, separate listings containing individual subject adverse event data may be provided.

5.4.1.2. TEAEs by System Organ Class and Preferred Term

The following summary tables of TEAEs will be provided by SOC and PT using frequency counts and percentages (i.e. number and percentage of subjects with an event):

- All unsolicited TEAEs
- All unsolicited TEAEs that are treatment-related
- All serious AEs
- All serious AEs that are treatment-related
- All unsolicited TEAEs leading to discontinuation from study vaccine (mRNA-1273 primary series only)
- All unsolicited TEAEs leading to discontinuation from participation in the study
- All unsolicited severe TEAEs
- All unsolicited severe TEAEs that are treatment-related
- All unsolicited AEs that are medically-attended

Summary tables of all unsolicited TEAEs, Serious AEs, treatment-related SAEs, MAAEs, and TEAE leading to discontinuation from participation in the study will also be provided by SOC and PT.

In addition, summary tables of select TEAEs of clinical interests identified by SMQ will be provided by PT.

Summary of AE of special interest per investigator's assessment will also be provided by SOC and PT.

5.4.1.3.Subgroup Analysis of TEAEs

An overview of TEAE, TEAE summaries presented by SOC and PT will be provided for the following subgroups:

- Age group (<65, and ≥ 65 years)
- Sex (male, female)
- Pre-booster SARS-CoV-2 status
- Race
- Ethnicity

These summaries may be provided for subgroups of select baseline characteristics.

5.4.2. Other Safety Endpoints Pregnancies

For Vital sign measurements, including systolic and diastolic blood pressures, heart rate, respiratory rate, and body temperature, the abnormalities meeting the toxicity grading criteria will be summarized .

A listing of pregnancies including outcome will be provided.

5.5. Immunogenicity Analysis

The secondary immunogenicity objective (Part A), to evaluate the immunogenicity of 2 doses of mRNA-1273 given 28 days apart, have been evaluated and summarized in the Part A CSR (dated 03 Aug 2021) using the Per-protocol stratified random subcohort (PPRSI). mRNA-1273 was highly immunogenic as measured by both bAb and nAb in both SARS-CoV-2 baseline-negative and baseline-positive individuals, as indicated by increased bAb and nAb levels 1 month after first injection (Day 29) and 1 month after second injection (Day 57).

This SAP includes analyses of immunogenicity data to evaluate the immunogenicity of mRNA-1273 primary series and booster.

In principle, summary (descriptive statistics) will be provided for available immunogenicity data by timepoints in relative of primary series and booster dose respectively. Comparison or analysis to assess difference between groups (Section 5.5.3) will only be performed using the same assay from the same (central) testing lab.

For immune response to a booster, Part C PPIS (Part C Per-Protocol Immunogenicity Subset), defined in Section 4.3, will be used for summaries of immune response, and data will be presented by pre-booster SARS-CoV-2 status. Part C PPIS-Neg, Part C PPIS – Pre-booster SARS-CoV-2 Negative defined in Section 4.4, will be used as the primary analysis population for comparison of immune response, either as paired-comparison when a subject serves as his/her own control; or between-group comparison compared to post-primary series in Part A using mRNA-1273 subjects in PPRSI with negative baseline SARS-CoV-2 as historical control.

